7.6.15.1. Screening (Days -28 to -8) Laboratory Tests

- Routine blood chemistry tests will include: glucose, total bilirubin, serum glutamic oxaloacetic transaminase/aspartate transaminase (SGOT/AST), serum glutamic pyruvic transaminase/alanine transaminase (SGPT/ALT), alkaline phosphatase, blood urea nitrogen, creatinine, amylase, total protein, uric acid, sodium, chloride, bicarbonate, potassium, calcium, phosphorous, albumin, triglycerides, cholesterol: low density lipoprotein (LDL) and high density lipoprotein (HDL).
- Routine hematology tests will include: white blood cell (WBC) with differential count, red blood cell (RBC), hematocrit, hemoglobin, and platelet count.
- Hepatitis B (HBsAg), hepatitis C (HCV-Ab) serology and human immunodeficiency virus (HIV) type 1 and 2.
- Urine drug screen for sympathomimetic amines (amphetamines; benzodiazepines; buprenorphine; cannabinoids; methadone; cocaine (metabolites); opiates (except barbiturates for AED medication).
- Blood test for the presence of ethanol.
- Urine specimens will be tested for routine urinalysis (specific gravity, pH, protein, glucose, ketones, bilirubin, blood, leukocyte esterase and nitrite) and microscopic analysis if indicated.
- Pregnancy test, females only (plasma or urine).
- Optional: DNA sample for genomic screening.

7.6.15.2. Week 6, Week 14, and Week 38 (±3 days) Laboratory Tests

- Routine blood chemistry tests will include: glucose, total bilirubin, SGOT/AST, SGPT/ALT, alkaline phosphatase, blood urea nitrogen, creatinine, amylase, total protein, uric acid, sodium, chloride, bicarbonate, potassium, calcium, phosphorous, albumin, triglycerides, cholesterol: LDL and HDL.
- Routine hematology tests will include: WBC with differential count, RBC, hematocrit, hemoglobin, and platelet count.
- Urine specimens will be tested for routine urinalysis (specific gravity, pH, protein, glucose, ketones, bilirubin, blood, leukocyte esterase and nitrite) and microscopic analysis if indicated.
- Pregnancy test, females only (plasma or urine).

7.6.15.3. End of Study Visit or Early Termination

- Each patient will have an End of Study Visit/ET completed at Week 38. The clinical laboratory testing will include the following:
- Routine blood chemistry tests will include: glucose, total bilirubin, SGOT/AST, SGPT/ALT, alkaline phosphatase, blood urea nitrogen, creatinine, amylase, total protein, uric acid, sodium, chloride, bicarbonate, potassium, calcium, phosphorous, albumin, triglycerides, cholesterol: LDL and HDL.

- Routine hematology tests will include: WBC with differential count, RBC, hematocrit, hemoglobin, and platelet count.
- Urine specimens will be tested for routine urinalysis (specific gravity, pH, protein, glucose, ketones, bilirubin, blood, leukocyte esterase, and nitrite) and microscopic analysis if indicated.
- Pregnancy test, females only (plasma or urine).

7.6.16. Unscheduled Visits

If the skin irritation score is >'0' at Week 38, and weeks 40 or 41 for patients taking AED medications, the patient will have Unscheduled Visit(s) until the skin irritation score is rated as '0' (no erythema). The following assessments will be completed at the Unscheduled Visit:

- Concomitant medication review
- Vital signs
- C-SSRS
- Site review of patient Skin Irritation Diary
- Skin irritation examination
- Adverse event review

7.6.17. Hepatitis/HIV Screen

At the Screening Visit patients will be screened for HBsAg, HCV-Ab serology and HIV type 1 and type 2.

7.6.18. Pregnancy Test

Pregnancy tests will be collected at Screening, Week 6, and Week 14/EOS/ET Visits for female patients of child bearing potential. Any patient that is pregnant will be excluded or discontinued from the study, as applicable. Pregnancy test can be plasma or urine.

7.6.19. Toxicology Screen

Urine drug screen for sympathomimetic amines (amphetamines; benzodiazepines; buprenorphine; cannabinoids; methadone; cocaine (metabolites); and opiates (except barbiturates for AED medication) will be done at Screening. In addition, a blood test for the presence of ethanol will be done at Screening. A positive toxicology screen will result in excluding the patient from the study.

7.6.20. Blood Samples for Valproic Acid

At Screening, Week 6, Week 14, and Week 38 EOS/ET Visits, patients will have blood drawn for plasma level of their valproic acid (for patients receiving valproate or valproic acid).

All effort should be made to obtain a trough sample for the valproate/valproic acid. AED name, time taken, and amount and date of the last dose will be captured before the blood samples are collected. At each monthly visit, the Investigator will review the valproic acid (for patients receiving valproate or valproic acid) level and the dose of concomitant AEDs in the event they require adjusting if the patient experiences AEs that warrant a dose change.

7.6.21. Blood Sample for CBD/THC PK

At the Screening Visit, Week 6/Visit 3 and Week 14/Visit 4, and Week 38/Visit 7 EOS/ET, blood will be drawn for a trough plasma level for the determination of CBD/THC. All PK blood samples will be collected pre-dose.

7.6.22. Telephone Follow-up at Week 10

There will be a Telephone Follow-up call at Week 10 only for patients who had their dose adjusted at Week 6. The purpose of the call is to confirm the patient is tolerating the increased dose. Concomitant medications and adverse events will be reviewed at the Telephone Follow-up call, along with enquiring about patient skin irritation.

7.7. Study Questionnaires and Scales**7.7.1. Assessments of 22qDS Symptomatology**

The same site rater should be used for all clinician-reported assessments across all visits. The same parent/caregiver should be used for all parent/caregiver-reported assessments across all visits.

7.7.2. Aberrant Behavior Checklist-Community (ABC-C)

The Aberrant Behavior Checklist- Community, 2nd Edition, will be completed by the parent/caregiver, with support from the site staff, at Screening, Visit 2, Visit 3, Visit 4, Visit 5, Visit 6, and Visit 7 EOS/ET. The ABC-C asks responders to rate behaviors from “0 - not at all a problem” to “3 - the problem is severe in degree” across 58 questions. Use of the checklist has been validated in a variety of clinical populations.

7.7.3. Autism Diagnostic Observation Schedule[®] (ADOS[®]-2)

The ADOS (Western Psychological Services) is a semi-structured assessment of communication, social interaction and play or imaginative use of materials for individuals suspected of having 22qDS or other pervasive developmental disorders from 12 months through adulthood (Lord et al. 2000). The ADOS[®]-2 consists of various activities to allow the observation of social and communication behaviors related to the diagnosis of pervasive developmental disorders. The ADOS[®]-2 includes five modules for use with different age groups and language level. In this version, a Toddler Module has been included. For this patient population, the appropriate module will be utilized based on age and language level. Each subject will be administered one module. The assessment is administered by a certified rater and requires 35 to 40 minutes to complete. The ADOS[®]-2 is a diagnostic tool and this information will be used to document the presence of autism or other pervasive developmental disorders. This assessment will only be administered at sites with qualified individuals based on the publisher’s criteria. The ADOS[®]-2 will be completed at Screening.

7.7.4. Clinical Global Impressions Scale-Severity and Improvement

The Clinical Global Impression Scales, Severity (CGI-S) and Improvement (CGI-I), are commonly used in clinical trials (Leigh et al. 2013) as they allow the clinician to utilize the history from the caregiver and incorporate the score into a clinical rating for the severity of symptoms.

CGI-S is a 7-point scale that requires the clinician to rate the severity of the patient's illness at the time of assessment, relative to the clinician's past experience with patients who have the same diagnosis. Considering total clinical experience, a patient is assessed on severity of mental illness at the time of rating 1 - normal, not at all ill; 2 - borderline mentally ill; 3 - mildly ill; 4 - moderately ill; 5 - markedly ill; 6 - severely ill; or 7 - extremely ill. CGI-S will be assessed at Screening, Visit 2, Visit 3, Visit 4, Visit 5, Visit 6, and Visit 7 EOS/ET to judge the severity of the symptoms of 22qDS at the onset of and throughout the study.

CGI-I is a 7-point scale that requires the clinician to assess how much the patient's illness has improved or worsened relative to a Baseline state at the beginning of the intervention and rated as: 1 - very much improved; 2 - much improved; 3 - minimally improved; 4 - no change; 5 - minimally worse; 6 - much worse; or 7 - very much worse. Information from both the clinician and the parent/caregiver history are incorporated into a clinical rating. CGI-I will be assessed at Visit 3 and Visit 4/EOS/ET.

7.7.5. Columbia Suicide Severity Rating Scale (Children's Version)

The C-SSRS (Children's version) is to be completed at Screening, all study visits including Unscheduled Visits. The C-SSRS assessment will be conducted only if the patients are of an appropriate age (6 years or older) and capable of understanding and answering the questions in the Investigator's opinion. For patients under the age of 6 or who are not capable of understanding and answering the questions in the Investigator's opinion, the Investigator will consider the trend in ABC-C Irritability when assessing the risk of self-harm for an individual patient.

Any patient who responds Yes to Questions '4' or '5' on the C-SSRS will be discontinued from the study and the Investigator will determine if further evaluation is required. Note that any completed suicide or suicidal attempt will be collected as an SAE.

7.7.6. Anxiety, Depression, and Mood Scale (ADAMS)

The Anxiety, Depression, and Mood Scale will be completed by the parent/caregiver, with support from the site staff, at Screening, Visit 2, Visit 3, Visit 4, Visit 5, Visit 6, and Visit 7 EOS/ET. The ADAMS will be used as a comprehensive assessment of anxiety, depression, and mood among the FXS patients. The ADAMS is comprised of 28 items, which are rated on a scale of "0 - not a problem" to "3 - severe problem." The ADAMS yields a total score as well as five subscale scores: "Manic/Hyperactive Behavior," "Depressed Mood," "Social Avoidance," "General Anxiety," and "Compulsive Behavior." The ADAMS has been validated and has demonstrated good internal consistency and test-retest reliability. Interrater reliability has been shown to be satisfactory (Esbensen et al. 2003).

7.7.7. Qualitative Caregiver Behavioral Problems Survey

At the Screening Visit, the parent/caregiver will be asked the following question “What are the three behavioral, emotional, or social problems that most impacted your son/daughter and his/her family in approximately the past year?” At Visit 3, Visit 4, Visit 5, Visit 6, and Visit 7 EOS/ET the parent/caregiver will be reminded of their responses at the Screening Visit in order to rate the three questions for improvement or worsening.

7.7.8. Children’s Sleep Habit Questionnaire (CSHQ)

The Children’s Sleep Habit Questionnaire will be completed by the parent/caregiver at Screening Visit 4, and Visit 7 EOS/ET. The parent/caregiver will complete a questionnaire comprised of 33 questions about their child’s sleep habits and possible difficulties with sleep. They will be asked to think about the past week in your child’s life when answering the questions. If last week was unusual for a specific reason (such as their child had an ear infection and did not sleep well or the TV set was broken), they will choose the most recent typical week. They will:

- Answer USUALLY if something occurs 5 or more times in a week.
- Answer SOMETIMES if it occurs 2-4 times in a week.
- Answer RARELY if something occurs never or 1 time during a week.

Parent/caregiver will also indicate whether or not the sleep habit is a problem by circling “Yes”, “No,” or “not applicable (N/A)”.

7.7.9. Pediatric Anxiety Rating Scale – Revised (PARS-R)

The PARS-R will be completed at Screening, Weeks 14, 22, 30, and Week 38. The patient must have a severity score of 10 or higher at Screening and Visit 2 in order to be eligible for participation.

The PARS-R is a clinician-rated caregiver interview that covers 61 behaviors related to anxiety (Riddle, Ginsburg, Palapattu, & Walkup 2004, Riddle et al. 2002). The PARS-R provides broad coverage of separation anxiety, social phobia, and generalized anxiety. Symptoms are further categorized into Social Interactions or Performance Situations, Separation, Generalized, Specific Phobia, Panic Symptoms/Physical Signs, Obsessive-Compulsive, Health/Illness Concerns, and Other. The interviewer assesses the severity by quantifying the frequency and degree of interference and avoidance in family, school and community settings. Each of seven severity items is scored on a scale of 1 to 5, with 5 being the most severe and frequent. The final score is the sum of five of the seven severity items. The five item scale is recommended for use during treatment studies (Riddle et al. 2004, Riddle et al. 2002). Studies show excellent inter-rater reliability (even across sites kappa .87-.90) and test retest reliability after 3 to 8 weeks in 49 individuals with FXS ages 5 to 35 years of age (Russo- Ponsaran et al. 2014 AJIDD). The PARS-R correlates well with other anxiety measures (Russo-Ponsaran et al. 2014) and has been used in clinical trials in individuals with Autism Spectrum Disorder ASD (Storch et al. 2014) and is currently being utilized in several trials in FXS.

7.8. End of Study / Early Termination Visit

All patients will complete the EOS/ET Visit assessments at Week 38. Patients not taking AEDs will only have a morning dose of study drug at the Week 38 Visit before discharge from the study. The following will be completed at the EOS/ET Visit:

- Laboratory and urinalysis tests as defined in Section 7.6.15.3.
- Concomitant medication review
- Physical/neurological examination
- Vital signs
- 12-lead ECG
- Pregnancy test (females only)
- Collection and site review of patient Daily Skin Irritation Diary (diary for AED patients will also be collected Week 16 or 17)
- CBD/THC plasma sample drawn
- Valproic acid plasma sample drawn (for patients taking valproate or valproic acid)
- Skin irritation examination
- Adverse event review
- Completion of patient questionnaires and scales – refer to Table 5 and Table 6 in Section 7.7
- Study drug will be applied (last dose for patients not taking AED medication, not applicable to ET patients)

Patients not on AEDs who are prematurely discontinued will complete the early termination procedures at Visit 7 EOS/ET.

Patients taking valproate or valproic acid for treatment of seizures or epilepsy including patients who prematurely discontinue, will taper their current study dose in the following manner beginning at Visit 7 EOS/ET. Should patients taking AEDs at the EOS continue to receive drug through Special Access (if available) they will not taper their dose.

- Participants who weigh 35 kg or less and were receiving 250 mg daily dose of ZYN002, will be reduced to 125 mg daily dose over one week. Only one sachet will be applied each day around the same time in the evening. After the taper, the participants will discontinue from the study at Week 40.
 - If the participant's dose was increased at Week 6 to 500 mg daily dose of ZYN002, the dose will be reduced to 250 mg daily dose over one week with 2 sachets applied each day around the same time in the evening. After the taper, the participants will discontinue from the study at Week 40.
- Participants who weigh 35 kg or more and were receiving 500 mg daily dose of ZYN002, will be reduced over two weeks. During the first week the dose will be reduced to 125 mg two times a day (applied 12 hours apart) which will make the total daily dose 250 mg. This is one sachet in the morning and one sachet in the evening. During the second week, the dose will decrease to 125 mg daily dose, which means one sachet each day for a week applied each day around the same time in the evening. After the taper, the participants will discontinue from the study at Week 41.

- If the participant's dose was increased at Week 6 to 750 mg daily dose of ZYN002, the dose will be reduced to 375 mg daily dose during the first week with one sachet applied in the morning and 2 sachets applied every evening. During the second week, the dose will decrease to 250 mg daily dose, which means 2 sachets each day for a week applied each day around the same time in the evening. After the taper, the participants will discontinue from the study at Week 41.
- Patients tapering their dose will have all Visit 7 EOS/ET assessments completed.
- At Week 38, patients will have their original dose in the morning and will have their evening dose as their new tapered dose.
- Patients will return at Week 40 or 41 and have the following assessments completed:
 - Concomitant medication review
 - Vital signs
 - Targeted physical exam if investigator deems clinically relevant
 - Pregnancy test (females only)
 - C-SSRS administered
 - Collection and review of Skin Irritation Diary
 - Skin irritation examination
 - Adverse event review

Patients having a skin irritation score > '0' at Week 38 will continue to be followed through Unscheduled Visits until the skin irritation score is recorded as '0' (no erythema).

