Patients should keep the application site dry for six hours but may apply an approved moisturizing lotion (Cetaphil), provided by the Sponsor, two hours after dosing. The application site should be covered to minimize sun exposure when going outside during the day. Sunscreen at the application site may be used two hours after dosing. If excessive skin irritation occurs at the application site, the parent (after consultation with the Investigator) may switch the application site temporarily to the upper thighs.

Patients who weigh ≤ 35 kg will receive 125 mg CBD Q12H (every 12 hours) (± 2 hours); for a total daily dose of 250 mg CBD. Patients who weigh > 35 kg will receive 250 mg CBD Q12H (± 2 hours); for a total daily dose of 500 mg CBD. All patients will remain on their assigned dose through Week 6. At Week 6, if the patient has less than a 25% improvement from baseline in the ABC-C irritability subscale, the investigator may increase the dose, as follows:

- Patients who weigh ≤ 35 kg receiving a total daily dose of 250 mg CBD may increase to a daily dose of 500 mg.
Patients who weigh > 35 kg receiving a daily dose of 500 mg CBD may increase the dose to 750 mg/day.

The following questionnaires and scales will be administered at Visit 2, Visit 3, Visit 4, Visit 5, Visit 6, and Visit 7 EOS/ET, unless an exception is noted:

- ABC-C
- CGI-S
- Clinical Global Impression-Improvement (CGI-I) (not completed on Visit 2, Day 1)
- ADAMS
- C-SSRS
- Qualitative Caregiver Reported Behavioral Problems Survey (not completed at Visit 2)
- Children's Sleep Habit Questionnaire (Visit 4 and Visit 7 EOS/ET only)
- PARS-R

End of Study (EOS) / Early Termination Visit (ET):

Patients not on AEDs who are prematurely discontinued or do not qualify for Period 2, will complete the early termination procedures at Visit 4 EOS/ET.

Patients taking valproate or valproic acid for the treatment of seizures or epilepsy, including patients who prematurely discontinue, will taper their current study dose in the following manner beginning at Visit 7 EOS/ET. Should patients taking AEDs at the EOS continue to receive drug through Special Access (if available) they will not taper their dose.

- Participants who weigh 35 kg or less and were receiving 250 mg daily dose of ZYN002, will be reduced to 125 mg daily dose over one week. Only one sachet will be applied each day around the same time in the evening. After the taper, the participants will discontinue from the study at Week 40.

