| Pregnancy Test ^d | | | X | | | X | |
| CBD/THC PK Blood Sample | | | X | | | | |
| Blood Sample for Valproic Acid ^{e, g} | | | X | | | | |
| ABC-C | X | X | X | | | | |
| CGI-S | X | X | X | | | | |
| CGI-I | X | X | X | | | | |
| ADAMS | X | X | X | | | | |

Table 6: Period 2 Schedule of Assessments – 24-Week Extension Treatment Period, cont'd

| Study Procedures | 24-Week Treatment Period – Visit Schedule | | | Taper Period, If Applicable | | Study Visit Week 40 or Week 41 for AED Patients Tapering Study Drug ^a Visit ^a | Un-scheduled Visit(s) |
|--|---|--------------------------------------|---|--|---------------------------|--|--------------------------|
| | Visit 5 Week 22 (± 3 days) | Visit 6 Week 30 (± 3 days) | Visit 7 Week 38 EOS/ET ^a (± 3 days) | Week 39 (± 3 days) | Week 40 (± 3 days) | | |
| | Study Drug Dosing | | | Tapered 50% each week. No Study Visit | | | |
| C-SSRS | X | X | X | | | X | X |
| Qualitative Caregiver Behavioral Problems/Improvements Survey | X | X | X | | | | |
| Children’s Sleep Habit Questionnaire | | | X | | | | |
| Pediatric Anxiety Rating Scale-Revised | X | X | X | | | | |
| Daily Study Drug Application | X | X | X | X | X | | |
| Parent/caregiver Completes Daily Skin Irritation Diary ^{f, h} | X | X | X | X | X | X | X |
| Review Patient Skin Irritation Diary | X | X | X | | | X | X |
| Skin Irritation Exam ⁱ | | | X | | | X | X |
| Adverse Event Review | X | X | X | | | X | X |

Table 6 Footnotes - Period 2:

- a. Patients who withdraw prior to Period 2 Week 38 will complete the EOS/ET at Week 38. AED patients will taper study drug for 1 or 2 weeks after the EOS Visit and return on Week 40 or 41 for final discharge from the study, unless they are transitioning to receive drug through Special Access.
- b. Patients will have both weight and height taken at EOS/ET. For patients taking AEDs and returning on Week 40 or 41 to be discharged from the study, a targeted physical examination (heart, lungs, abdomen and extremities) may be performed, if the investigator deems clinically relevant.
- c. Vital signs (including blood pressure, heart rate, respiratory rate, and infrared forehead or oral or tympanic temperature) will be recorded after the patient has been sitting for at least 5 minutes. Vital signs will be assessed at each study visit pre-dose.
- d. A pregnancy test will be completed at Week 38/EOS/ET for all females of childbearing potential. Pregnancy tests can be plasma or urine.

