8.4. Patient Withdrawal Criteria

Each patient has the right to withdraw from the study at any time without prejudice. If a patient withdraws from the study after receiving study drug, the reason(s) must be stated on the CRF, and a final evaluation of the patient should be performed.

The Investigator and/or Sponsor may discontinue any patient’s participation for any reason including (not all inclusive): any adverse event, clinically significant worsening in seizure frequency, adverse change in any laboratory test, or failure to comply with the protocol. Laboratory samples for a post-study laboratory profile and follow-up safety exams should be obtained as soon after patient discontinuation as possible.

Patients who withdraw from the study will not be replaced. All effort must be made to ensure that the End of Study/Early Termination Visit procedures are completed at the time of discontinuation.

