5.2. Data included in Period 1 Analyses

The records to be included in the Period 1 analyses will include all records with a nominal visit of ≤ 4 (Week 14/ET). All summaries will include one column only identified as ZYN002.

In an attempt to include all Period 1 Concomitant Medications and Adverse Events in the Period 1 analyses TGG will need to calculate a Week 14 Date for both subjects who completed Period 1 and who discontinued in Period 1 before Week 14. This will be accomplished by the following steps using the last non-missing value as the actual or imputed Week 14 date:

- a) If a subject completes Period 1 then use their actual Week 14 Date.
- b) If a subject discontinues before Week 14 date and their last nominal visit is identified as Week 14/ET then add ‘X’ days to that date to get to Day 98 (7 times 14).
- c) If Week 6, TGG will impute the Week 14 cutoff date to be the Week 6 date plus (7 times 8) to get the Week 14 imputed Date

d) If Day 1, TGG will impute the Week 14 date to be Day 1 plus (7 times 14)

Treatment emergent adverse events and concomitant medication summaries will include start dates that occur any time before treatment begins and treatment ends. Refer to [Section 6.2.3](#).

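### The protocol conflicts on the label and timing of the early-termination visit, and a Period 1 dropout's ET record filed as Section 7.8 directs would fall outside the Period 1 visit-based analyses

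*Protocol*

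**What the plan says.** On the visit label:

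- Protocol 7.8: prematurely discontinued patients not on AEDs "will complete the early termination procedures at Visit 7 EOS/ET". No period is named.
- Protocol synopsis, repeated in the SAP synopsis: patients not on AEDs who stop early or do not qualify for Period 2 "will complete the early termination procedures at Visit 4 EOS/ET".
- Protocol Table 5 footnote a (Period 1), repeated in the SAP: every patient has a Week 14/ET visit.

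On timing:

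- Protocol 7.6.15.3: "Each patient will have an End of Study Visit/ET completed at Week 38". The opening of Section 7.8 likewise puts everyone's EOS/ET assessments at Week 38.
- Protocol Table 6 footnote a, under the Period 2 footnotes: "Patients who withdraw prior to Period 2 Week 38 will complete the EOS/ET at Week 38".
- Protocol 8.4: all effort is to be made so that "End of Study/Early Termination Visit procedures are completed at the time of discontinuation".

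On the analysis, SAP 5.2 states: "The records to be included in the Period 1 analyses will include all records with a nominal visit of" 4 or lower, which it labels Week 14/ET. For adverse events and concomitant medications it adds a cut-off at an actual or imputed Week 14 date. The steps for that date cover patients who completed Period 1 and dropouts whose last nominal visit is Week 14/ET, Week 6 or Day 1. SAP 6.7.1 (ABC-C) and 6.7.2 (CGI-S) analyse Weeks 6, 14, 22, 30 and 38/ET, so there the ET label is attached to Week 38.

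**The concern.** SAP 6.7 makes the change from baseline to the end of Period 1 the first efficacy step and lets it guide the further exploratory analyses. About 20 patients are planned and dropouts are not replaced, so each record counts.

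The Period 1 filter works on the nominal visit. An ET record labelled Visit 7 fails it even if the patient stopped in the first weeks. The date rule in SAP 5.2 rescues adverse events and concomitant medications but not the visit-based data: efficacy scales, laboratory results and the C-SSRS, all of which SAP 5.1 lists for the interim analysis.

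The same record could then be summarised at Week 38. Apart from ET records, that row holds only patients who entered Period 2 by improving at least 35% on ABC-C irritability.

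**Working it through.** The plan states no dropout rate, effect size or sample-size calculation, so there is no figure of its own to reproduce. The check applies the SAP 5.2 filter to a patient who stops in Period 1, under each possible label.

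| Patient stops | ET labelled | Kept in Period 1 | Post-baseline visits kept |
|---|---|---|---|
| Before Week 6 | Visit 4 | Screening, Day 1, ET | 1 |
| Before Week 6 | Visit 7 | Screening, Day 1 | 0 |
| Weeks 6 to 14 | Visit 4 | Screening, Day 1, Week 6, ET | 2 |
| Weeks 6 to 14 | Visit 7 | Screening, Day 1, Week 6 | 1 |

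If 0 to 4 of 20 patients (assumed) stop before Week 6 and are filed under Visit 7, the number with any Period 1 post-baseline efficacy visit runs from 20 down to 16, a loss of 0% to 20%.

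**Distance in time.** Week 14 is Day 7 x 14 = 98 and Week 38 is Day 7 x 38 = 266. A Period 1 ET shown at Week 38 would be placed nominally at least 266 - 98 = 168 days too late.

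**Effect on the Week 14 mean.** Assumptions: 20 patients; d dropouts, all filed under Visit 7; mean change -6 in completers and m in dropouts; and ET values would otherwise count at Week 14. The value d = 2 matches the sponsor's earlier 12-week open-label Fragile X study (Protocol 5.3.2), where 18 of 20 completed; d = 1 and d = 4 give a range. The -6 is illustrative.

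All-patient mean = [(20 - d) x (-6) + d x m] / 20; reported mean = -6.0.

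With m = 0:

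- d = 1: 19 x (-6) / 20 = -5.7; 6.0 / 5.7 = 1.05
- d = 2: 18 x (-6) / 20 = -5.4; 6.0 / 5.4 = 1.11
- d = 4: 16 x (-6) / 20 = -4.8; 6.0 / 4.8 = 1.25

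With m = -6 the all-patient mean is -6.0 for every d, a ratio of 1.00. If dropouts had improved by more than 6 points, the reported mean would be too small.

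**The case against.** The strongest reply is that the analysis plan already expects a Period 1 ET at Visit 4. The Table 5 column is headed Visit 4, Week 14, EOS/ET. The SAP repeats that column, its footnote and the synopsis rule, and does not repeat the 7.8 sentence. SAP 5.2 labels its own filter Week 14/ET and has a step for a dropout recorded that way. The recorded label comes from the CRF, which is not available here, and SAP Table 2 gives ET its own column. All of this stands, and it makes the loss conditional. It does not remove the conflict: 7.8 is the section devoted to this visit, its wording is not limited to Period 2, and SAP 6.7.1 and 6.7.2 give a programmer a second place for an ET record.

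Four stronger readings are tempting but not supported:

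- **Four different ET visits.** Visit 7 is Week 38, Table 6 footnote a belongs to Period 2, and Section 8.4 gives a time that fits either label. There are two conflicts: Visit 4 against Visit 7, and Week 38 against the time of discontinuation.
- **The dropout is lost.** Only the ET record is. Disposition, baseline and any Week 6 data remain.
- **Period 1 safety data are lost in general.** Adverse events and concomitant medications are selected by date. For the C-SSRS, SAP 5.1 lists it for the interim but SAP Section 11 does not mark its summary table for Period 1.
- **The mean is biased towards completers by 11%.** That is one assumed scenario. Nor is -5.4 plainly the right Week 14 mean, since it counts values taken before Week 14 as Week 14 values.

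**Conclusion.** The point holds in a limited form. The protocol contradicts itself on the label and the timing of the ET visit. If Section 7.8 is followed literally for a Period 1 dropout, the ET record's visit-based data fall outside the Period 1 analysis and may appear at Week 38. A dropout before Week 6 then has no Period 1 post-baseline efficacy record; a later one loses only the ET record.

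Whether this happened depends on which text the sites followed, which the documents do not show. The effect on the mean is unknown in size and direction. The range of 0% to 25% rests on the assumed changes and dropout numbers and on every affected ET being filed under Visit 7. Correction is still worthwhile: the trial is small, the rule is in the text, and consistent wording costs almost nothing.

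**What to change.** 1. **Protocol.** Reconcile the synopsis, Table 5 footnote a, Table 6 footnote a, and Sections 7.6.15.3, 7.8 and 8.4 to one ET timing and one visit label per period. Carry the result into the SAP's copies of the synopsis and footnotes.
2. **SAP 5.2, 6.7.1 and 6.7.2.** State that an ET on or before the actual or imputed Week 14 date belongs to Period 1 (Week 14/ET) and a later one to Period 2, whatever visit label was recorded, and that a Period 1 ET is never tabulated under Week 38. Changing the 5.2 filter alone is not enough, because a record labelled Visit 7 would still be summarised at Week 38.
3. **SAP 5.2 date steps.** Add a step for a dropout whose ET was recorded as Visit 7; there is none now.

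The cost is some wording, one assignment rule and one extra derivation step. The Note to File at the front of the SAP says that neither document will be updated. If that stands, check the recorded visit of each Period 1 ET and document its assignment in a further note to file or in the study report.
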